	
triggered by causes such as acute coronary syndrome, pulmonary embolism, cerebrovascular accident, heart valve disorders (such as severe aortic stenosis), as determined by the Investigator
	

Sections: Clinical trial summary in statistical considerations and in study design            Also; Section 14.10 Interim analyses
	
Remove reference to interim analyses
	
The IA was originally intended to assess safety and to consider whether the number of subjects needs to be increased going forward with cohort 3. Accumulating favorable safety data in the CHF in this study and other ongoing studies with larger number of subjects and longer exposure obligated the need to study the lower dose of 200mg. Therefore the number of the remaining subjects who are on 400 mg is too small for a meaningful IA. Hence the IA was removed.

Section 13.1.4 Study restrictions
	
In cohort 3 remove the requirement to eat 15 minutes after IMP administration
	
Investigators note that this is difficult for the subjects to comply and record feed times

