## 8 SELECTION OF PATIENTS

### 8.1 NUMBER OF PATIENTS PLANNED

The study population will consist of male and female patients, 18 years and older, admitted to the hospital or heart failure unit or infusion center with worsening of heart failure requiring administration of intravenous diuretics, as per inclusion and exclusion criteria detailed below.

A subject who received treatment and prematurely ends his/her treatment will be replaced in order to have approximately 64 evaluable observations.

A patient should not be randomized more than once.

Re-screening is allowed once during the current hospitalization, if in the opinion of the investigator, the change in the clinical status of the patient allows inclusion in the trial. Patients that failed screening during the first encounter for this trial can be rescreened during subsequent hospitalizations or visits to the infusion or heart failure units.

A patient that requires re-hospitalization will be discontinued from IMP administration. Every effort will be made to follow up the progress of the patient and continue collection of relevant safety data, as appropriate and when applicable, and as judged by the Investigator with potential input from the DMC and Sponsor, as appropriate for each case, for the same follow up period (approximately 2 weeks) as for all other patients participating in the trial. In those cases, the follow up procedures and/or visit to clinical site should be followed as per study flow chart in [Section 1.2](#). Only if judged appropriate by the Investigator and Sponsor, and in the absence of safety signals, the patient will be allowed to participate in some or all of the EOT study procedures.

For all patients, GFR will be calculated from the serum creatinine (sCr; mg/dL) and age (years) via the abbreviated Modification of Diet in Renal Disease (MDRD) equation (20):

$$GFR = 186 (sCr)^{-1.154} (age)^{-0.203} (1.212 \text{ if black}) (0.742 \text{ if female})$$

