## 9.4 METHOD OF ASSIGNING PATIENTS TO TREATMENT GROUP

The randomized treatment kit number is generated centrally by Sanofi. The IMPs are packaged in accordance with this list.

At the Screening Visit, the Investigator or designee has to contact the IRT to receive the patient number. [REDACTED]

Before randomizing a subject on Day 1, the Investigator or designee should check if patients comply with all inclusion/exclusion criteria. At day 1, the IRT is contacted for randomization and corresponding allocation of treatments package. Patients are randomized to receive either sotagliflozin or placebo, according to the randomization scheme for each Cohort as described below:

Cohort 1: Sotagliflozin 200 mg: Placebo 2:1

Cohort 2: Sotagliflozin 400 mg: Placebo 2:1

Cohort 3 (as amended here): Sotagliflozin 400 mg: Placebo 1:1

For each randomized patient, the IRT will allocate a treatment package number corresponding to the treatment group assigned.

A randomized subject is defined as a subject who is registered and assigned with a treatment kit number from the IRT, as documented in IRT.

A subject cannot be randomized more than once in the study.

A patient can be rescreened once in case of manageable exclusion as deemed by the Investigator. In these cases, a patient will need to sign a new ICF, be registered as a new patient in IRT, and assigned a new patient number in IRT (first Screening Visit is to be registered as a screen failure in IRT), and complete the Screening Visit procedures/assessments again.

Potential replacement patients will have a patient number assigned from IRT and the patient number that is replaced will be recorded in IRT and transferred to the case report form. Each patient will receive the same treatment and treatment sequence as the withdrawn patient. See also [Section 12.3](#).

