### 12.3 REPLACEMENT OF PATIENTS

According to the study design, a patient who prematurely ends his/her study period after the start of the baseline period and who received treatment may be replaced in order to have 81 patients who have completed a minimum of 12 days treatment with IMP (sotagliflozin or placebo).

In the case of a discontinuation related to an AE, the replacement may be discussed between the Investigator and the Sponsor.

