## **14.10 INTERIM ANALYSIS**

Except DMC safety review planned after cohort 1 and cohort 2, there are no planned interim analysis.

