1.1 STUDY DESIGN AND RANDOMIZATION

This is a phase 2, multi-center, multinational, randomized, double-blind, placebo-controlled, parallel arm trial of the safety, tolerability and pharmacodynamic activity of sotagliflozin in hemodynamically stable patients with worsening heart failure. An initial cohort of patients (Cohort 1) will receive sotagliflozin 200mg (n=approximately 10) or placebo (n= approximately 5) for fourteen days. Following safety monitoring and review by the data monitoring committee (DMC), Cohort 2 will receive sotagliflozin 400mg (n= approximately 10) or placebo (n= approximately 5) orally for fourteen days. Following completion of Cohort 2 and review of safety and tolerability by the DMC, patients in Cohort 3 will be allocated to sotagliflozin 200 mg, (n= approximately 17) 400 mg (n= approximately 17) or placebo (n= approximately 17) orally for fourteen days. This is summarized in [Table 1](#).

Table 1 - Cohort randomization and allocation scheme

Cohort	Randomization	Sotagliflozin 200 mg	Sotagliflozin 400 mg	Placebo	Total N
1	2:1	10	0	5	15
2	2:1	0	10	5	15
3	1:1:1	17	17	17	51
Total N		27	27	27	81

Patients are randomized to receive either sotagliflozin or placebo, according to the randomization scheme for each Cohort as described below:

- Cohort 1: Sotagliflozin 200 mg : Placebo = 2:1
- Cohort 2: Sotagliflozin 400 mg : Placebo = 2:1
- Cohort 3: Sotagliflozin 200 mg : Sotagliflozin 400 mg : Placebo = 1:1:1

For each randomized patient, the IRT will allocate a treatment package number corresponding to the treatment group assigned.

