1.3 DETERMINATION OF SAMPLE SIZE

The sample size determination and the statistical power are estimated based on the main PD endpoint of plasma volume. The following assumptions are used for the estimation of the sample size, based on published data of the plasma volume (PV) response following 12 weeks of treatment with SGLT2 inhibition, relative to the placebo response, in non-HF patients:

- 10% reduction in plasma volume from baseline, with an averaged value of 0.47 liters difference for the sotagliflozin group to the end of 2-week treatment between the sotagliflozin and placebo groups, respectively;
- The placebo response might be highly variable in this population. In the study by Lambers Heerspink et al, PV increased by approximately 2% at the end of the 12 week treatment period in the non-HF population. For the purpose of sample size estimation in this study, the assumption is that PV will be reduced by 1% in the placebo group.
- A common standard deviation (SD) of 0.8 liters for the reductions from baseline to the end of 2-week treatment in plasma volume for both groups;
- A t-test at 1-sided $\alpha=0.05$; or equivalently, 2-sided $\alpha=0.10$;

Based on the above assumptions, it is estimated that, with a total of 81 patients with complete evaluations, or 27 patients per arm, the study will have a 71% power to detect an approximately 9 percentage point difference (10% vs 1%) in the reduction from baseline in plasma volume at the end of 2-week treatment for the main comparison of the pooled sotagliflozin (200 mg and 400 mg) group versus placebo. With 60 evaluable patients, or 20 patients per group, the study power is 60%. The calculated sample size refers to the size of completers who have plasma volume values at both baseline and end of the 2-week treatment.

[figure not shown]
Furthermore, interim analyses will be performed following Cohort 2 and during Cohort 3 for the purpose of exploratory analyses of pharmacodynamic, pharmacokinetic or safety variables, and sample size re-estimation, partly based on the observed variability of changes in plasma volume and/or hemoconcentration. Exploratory analyses may also be performed earlier for safety reasons, or if requested by the DMC or institutional ethics committees. In that case, the analysis will not result to any changes to the protocol.

The study population will consist of at least 30% diabetic patients.

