3 INTERIM ANALYSIS

Interim analyses will be performed following Cohort 2 and during Cohort 3 for sample size re-estimation or for the purpose of exploratory analyses. These planned interim analyses will focus on the main pharmacodynamic parameters of hemoconcentration and plasma volume. Descriptive statistics will be provided and ANCOVA analyses as described above will be performed for the interim analyses. Exploratory analyses may also be performed earlier for safety reasons, or if requested by the DMC or institutional ethics committees. In that case, the analysis will not result to any changes to the protocol.

The Statistician and Statistical Programmer will work independently to the study team on these interim analyses to ensure the blinding is preserved notably toward the Investigator. These analyses must provide only mean and variability data and exclude all individual information like minimum, maximum or median values and sample size per group. A dissemination plan of the results should be established upfront before the interim data unblinding.

The outcome of this interim analysis may lead to early termination of the trial, continuation without any changes, or continuation with changes.

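### The cut to 64 patients did not reach SAP 1.1, 1.3 and 3 or protocol 12.3; for the design now run, power on the SAP's own assumptions is about 66%, not 71%

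*SAP*

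**What the plan says.** **Sample size and power.** SAP 1.3 uses a one-sided 0.05 t-test with an SD of 0.8 L. Plasma volume is assumed to fall by 10% on sotagliflozin and 1% on placebo, and a figure of 0.47 L is attached to the sotagliflozin effect. With 81 completers, 27 per arm, "the study will have a 71% power to detect an approximately 9 percentage point difference (10% vs 1"%) for the pooled doses against placebo; with 60 evaluable patients, 20 per group, power is 60%. Protocol 14.1 says the size is empirical and not formally calculated.

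**Allocation.** SAP 1.1 has "Cohort 3: Sotagliflozin 200 mg : Sotagliflozin 400 mg : Placebo = 1:1:1", and its Table 1 totals 81. Protocol 9.4 has "Cohort 3 (as amended here): Sotagliflozin 400 mg: Placebo 1:1", and protocol Table 1 totals 64 (10 on 200 mg, 27 on 400 mg, 27 on placebo). Protocol 14.7.3 and SAP 2.6.2 both keep pooled sotagliflozin against placebo as the main comparison.

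**Replacement.** Under protocol 8.1 a patient who stops early "will be replaced in order to have approximately 64 evaluable observations". Under protocol 12.3 such a patient "may be replaced in order to have 81 patients who have completed a minimum of 12 days treatment with IMP".

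**Interim analysis.** SAP 3: "Interim analyses will be performed following Cohort 2 and during Cohort 3 for sample size re-estimation". Protocol 14.10: "Except DMC safety review planned after cohort 1 and cohort 2, there are no planned interim analysis". The summary of changes gives the reason for removal: "the number of the remaining subjects who are on 400 mg is too small for a meaningful IA".

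**Version.** SAP 1 names the protocol as amended on 14 Mar 2018. Amended Protocol 03 is dated 01-Aug-2019.

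**The concern.** Amended Protocol 03 removed the 200 mg arm from Cohort 3, which takes 17 patients out of the study. Most of the protocol reflects this, but section 12.3 and the SAP do not. Three things follow.

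- Sites and sponsor have two replacement targets, 81 and about 64. The wording also differs on whether replacement is mandatory and on what counts (evaluable observations, or at least 12 days of treatment).
- The study statistician has two interim plans. One includes sample-size re-estimation; the other has only the data monitoring committee's safety reviews.
- The only power figures in either document describe a 2:1 pooled split that no longer exists. If the plasma volume interval includes zero, SAP 1.3 is where a reader would look to judge how informative that is.

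**Working it through.** **Inputs**

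- One-sided alpha 0.05, t-test, common SD 0.8 L: SAP 1.3.
- Sotagliflozin reduction 10%, given as 0.47 L; placebo reduction 1%: SAP 1.3.
- Old pooled split: 27 + 27 = 54 vs 27 (81 patients), and 20 + 20 = 40 vs 20 (60 patients).
- Current pooled split: 10 + 27 = 37 vs 27 (protocol Table 1).

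**Difference in litres.** The 0.47 L bullet can be read in two ways. If 0.47 L is the 10% within-group fall, baseline is 0.47 / 0.10 = 4.7 L, and the 9-point difference is 0.09 × 4.7 = 0.423 L (0.42 L rounded). If it is the between-group difference, it is 0.47 L. Both are tested below.

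**Formulae.** SE = 0.8 × √(1/n₁ + 1/n₂); df = n₁ + n₂ − 2; noncentrality = difference / SE. Power is the probability that a noncentral t exceeds t(0.95, df). The 90% CI half-width is t(0.95, df) × SE.

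**Reproducing the SAP, then the current design**

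| Split | SE (L) | Power, 0.42–0.423 L | Power, 0.47 L | SAP states |
|---|---|---|---|---|
| 54 vs 27 | 0.189 | 71.3–71.9% | 79.6% | 71% |
| 40 vs 20 | 0.219 | 59.9–60.4% | 68.3% | 60% |
| 37 vs 27 | 0.202 | 65.8–66.3% | 74.2% | not given |

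For the pooled t-test that the SAP describes, only the within-group reading returns both stated powers. The 0.47 L reading comes near them (69.6% and 58.4%) only with a normal approximation and 27 vs 27 and 20 vs 20. That is neither the named test nor the pooled comparison.

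For 37 vs 27: SE = 0.8 × √(1/37 + 1/27) = 0.2025 L, df = 62, t(0.95, 62) = 1.670 and noncentrality = 0.423 / 0.2025 = 2.09, so power is 66.3%.

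**Precision.** The half-width is 1.664 × 0.1886 = 0.314 L for 54 vs 27, and 1.670 × 0.2025 = 0.338 L for 37 vs 27.

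**Missing plasma volume.** SAP 1.3 counts only patients with plasma volume at both visits. Protocol 10.1.2 limits the labelled-albumin method to sites able to perform it and lets patients decline. Replacement is triggered by stopping early, not by a missing plasma volume. The documents give no expected availability, so these shares are assumptions, equal across arms:

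| Share measured | Split | Power, 0.42–0.423 L |
|---|---|---|
| 90% | 33 vs 24 | 61–62% |
| 80% | 30 vs 22 | 58% |
| 70% | 26 vs 19 | 53% |

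**Covariate adjustment.** The planned model is an ANCOVA. If baseline and change correlate at r (an assumption), the residual SD is 0.8 × √(1 − r²). With all 64 patients, power is then 69–70% at r = 0.3 and 77% at r = 0.5.

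**400 mg against placebo.** All 27 placebo patients: 60–61%. Placebo patients from Cohorts 2 and 3 only (5 + 17 = 22): 56–57%.

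**The case against.** The strongest reply is that power hardly matters here. Protocol 14.1 disclaims a formal calculation, the ANCOVA is exploratory in protocol 14.7.3, no decision rule depends on power, and 66% lies between two figures the SAP already prints. The sensitivity range, 53% to 77%, even includes 71%. All of this stands as a limit on weight. It does not make 71% and 60% statements about the current design. SAP 2.6.2 also places the same ANCOVA under primary analysis.

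A related point is that a new power sentence would leave SAP 1.3 at odds with protocol 14.1. It need not: a power or precision statement for an empirically chosen size is consistent with 14.1 if the SAP says the size was empirical.

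It can also be said that the protocol carried the cut through nearly everywhere, and that 12.3 could not by itself add 17 patients. Under 9.4 each replacement takes the withdrawn patient's treatment, so replacing within 64 places never yields 81 completers. That limits the enrolment risk, but it also shows that 12.3 cannot be met as written.

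Finally, the corrected power reuses the SAP's effect assumptions. SAP 1.3 reports a placebo rise of about 2% in the 12-week study it cites; protocol 4.2.3, apparently describing the same study, gives 5.2%. The sponsor should check that. It does not change the calculation, which uses the assumed 1% fall.

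**Conclusion.** The concern holds. Protocol 12.3 contradicts 8.1 and Table 1 by 81 − 64 = 17 patients. The SAP's allocation, power figures and interim plan all describe the superseded design. For the 64-patient design, power for the pooled comparison is about 66% instead of 71%, and the expected 90% CI half-width rises from 0.31 to 0.34 L.

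The 66% rests on an unadjusted t-test, an SD of 0.8 L, 0.47 L read as the within-group fall, and plasma volume at both visits in all 64 patients. Missing measurements lower it; the ANCOVA may raise it. The change in power is modest and is not a design criterion here. The replacement target and the interim plan matter more in practice, and together they make this worth correcting.

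**What to change.** 1. **Protocol 12.3.** Reconcile the 81-completer target, and the optional against mandatory wording, with 8.1 and Table 1.
2. **SAP 1, 1.1 and Table 1.** Update to Amended Protocol 03. Remove the planned interim analyses and sample-size re-estimation from SAP 1.3 and 3, to match protocol 14.10.
3. **SAP 1.3, power.** State that the size is empirical, and replace the 81- and 60-patient sentences with:

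> With 64 patients having plasma volume at both visits (37 pooled sotagliflozin, 27 placebo), a between-group difference of about 0.42 L (10% vs 1%) and an SD of 0.8 L, an unadjusted t-test has about 66% power at one-sided 0.05, and the expected 90% CI half-width is about 0.34 L. Power is lower if plasma volume is not obtained in all 64; the ANCOVA may raise it.

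4. **SAP 1.3, effect size.** Reword the 0.47 L bullet as the 10% within-group reduction, subject to the sponsor's confirmation. If a figure for 400 mg against placebo is added, say which placebo patients it uses.

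The cost is a SAP revision and a protocol amendment for 12.3, which needs IRB/IEC approval under protocol section 18. The stated power becomes less favourable. No patients, visits or analyses are added.

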#### 10.1.2 Assessment methods

All eligible patients will have hemoconcentration samples obtained and total body water (deuterium oxide) assessment performed as per [Section 10.1.2.1](#) below.

Sites that have the capacity to perform the additional plasma volume assessment by the I-albumin method will follow the procedure described in [Section 10.1.2.2](#).

Patients who decline measurement of total body water or plasma volume by the indicator dilution methods, or in cases where in the opinion of the Investigator technical issues might prevent successful completion of those techniques, may still participate in the study provided they have measurements of plasma volume by the indirect hemoconcentration method.

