**Table 6 - Number of samples**

	I-albumin	Deuterium oxide
By subject / D 1	6	2
By subject / D 14	6	2
Total by subject	12	4
Total for study (approximately 64 patients)	approximately 768	approximately 256

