### **13.1.3.5 Visit 5 (Day 14±1)/**

Discharged Patients will return to the clinical site on day 14 ± 1 (Visit 5;). Exceptions can be made for those patients who may have been transferred to a step down unit, or rehabilitation ward or a different hospital. In those cases, plasma volume will not be assessed by the radiolabeled albumin method, unless the place is authorized for administration and collection of radioactive samples (such as a nuclear medicine facility) and has been discussed and approved by the relevant authority of the Institution(s) and Sponsor.

On days of site visits patients should be instructed not to take their dose of IMP in the morning of that day, as this will be administered by site staff as per the period flow chart in [Section 1.3](#).

The guidelines described above for Day 1 procedures and discharge, should also apply on day 14. Please refer to the study flow chart in [Section 1.2](#) and the period flow chart in [Section 1.3](#).

A patient who had plasma volume assessment performed on Visit 2 (Day 1) by the I-albumin method, should also have plasma volume assessment performed on Visit 5 by the I-albumin method (Day 14 ± 1).

A patient who *did not* have plasma volume assessment performed on Visit 2 (Day 1) by the I-albumin method, need *not* have plasma volume assessment performed on Visit 5 (Day 14 ± 1).

Patients should bring their Diaries, and relevant information will be transcribed to the eCRFs. New diaries will be dispensed.

The technique for measuring BP will be reviewed and further training provided as appropriate.

The Investigator will assess compliance with IMP.

IRT will be notified for end of treatment (EOT).

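### The SAP's 71% and 60% power count only patients with paired tracer plasma volumes, but neither the current 64-patient plan nor the replacement rules secure those numbers

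*SAP*

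**What the plan says.** SAP 1.3 bases power on plasma volume. The effect is introduced as "10% reduction in plasma volume from baseline, with an averaged value of 0.47 liters difference", with 1% reduction assumed on placebo, a common SD of 0.8 L and a one-sided 5% t-test of pooled sotagliflozin against placebo. It gives two figures, 71% for 81 patients and 60% for 60, and says whom they count: "The calculated sample size refers to the size of completers who have plasma volume values at both baseline and end of the 2-week treatment". SAP 2.6.1 defines the plasma volume endpoint in millilitres by labelled-albumin dilution.

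The SAP follows the protocol as amended in March 2018, with 81 patients. The current protocol (6.1, Table 1) plans 64: 10 on 200 mg, 27 on 400 mg and 27 on placebo. Its section 14.1 calls the sample size empirical and states no power.

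The tracer test is not universal:

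- Protocol 10.1.2 assigns it to "Sites that have the capacity to perform the additional plasma volume assessment by the" labelled-albumin method.
- The same section keeps in the study "Patients who decline measurement of total body water or plasma volume by the indicator dilution methods", and patients for whom technical problems are foreseen, provided hemoconcentration is measured.
- Protocol 13.1.3.5 covers patients moved to a step-down unit, rehabilitation ward or another hospital by Day 14: "In those cases, plasma volume will not be assessed by the radiolabeled albumin method, unless the place is authorized".

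On replacement, protocol 8.1 says: "A subject who received treatment and prematurely ends his/her treatment will be replaced in order to have approximately 64 evaluable observations". Section 12.3 allows replacement of patients who end the study period early, with a target of 81 patients having at least 12 days of treatment. Neither section mentions plasma volume.

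**The concern.** The stated power applies to a defined group, patients with two tracer values, and nothing in the plan sets or protects the size of that group. A patient who finishes treatment without a tracer pair triggers no replacement. Enrolment could therefore close on target with fewer pairs than the power statement assumes. Separately, the reduction from 81 to 64 patients was not carried into the SAP. At stake is the precision of the direct measure behind the co-primary pharmacodynamic objective, and whether a reader of SAP 1.3 is told what the current design can deliver.

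**Working it through.** **Inputs.** From SAP 1.3: SD 0.8 L, one-sided alpha 0.05, and 0.47 L attached to a 10% reduction. From protocol Table 1: 10 + 27 = 37 sotagliflozin and 27 placebo. Tracer uptake is not given, so it is an assumption, taken as equal across arms.

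**Formulas.** SE = 0.8 × √(1/n1 + 1/n2). Power is the probability that a noncentral t with n1 + n2 − 2 degrees of freedom and noncentrality delta/SE exceeds the 95th percentile of the central t. The 90% CI half-width is that percentile × SE.

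**Reproducing the SAP.** The SAP prints 0.47 L but says the difference to be detected is 9 percentage points. If 10% is 0.47 L, then 9 points is 0.9 × 0.47 = 0.423 L.

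- delta 0.423 L: 54 vs 27 gives 71.9% (stated 71%); 40 vs 20 gives 60.4% (stated 60%).
- delta 0.47 L: 54 vs 27 gives 79.6%; 40 vs 20 gives 68.3%. Neither matches.
- delta 0.47 L with one active arm: 27 vs 27 gives 68.6%; 20 vs 20 gives 57.1%. Neither matches as closely.

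So 0.423 L with pooled 2:1 allocation is the best reconstruction. It is derived, not printed.

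**Current allocation, by assumed uptake:**

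| Pairs (sotagliflozin vs placebo) | SE (L) | Power, delta 0.423 L | Power, delta 0.47 L | 90% CI half-width (L) |
|---|---|---|---|---|
| 37 vs 27 (all 64) | 0.203 | 66% | 74% | 0.34 |
| 28 vs 20 (75%) | 0.234 | 55% | 63% | 0.39 |
| 19 vs 14 (about half) | 0.282 | 43% | 49% | 0.48 |

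First row worked: 0.8 × √(1/37 + 1/27) = 0.2025; 0.423/0.2025 = 2.09; critical t on 62 df = 1.670; power 66.3%; half-width 1.670 × 0.2025 = 0.338 L.

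**Separating the two causes.** The step from 71% to 66% comes wholly from planning 64 instead of 81. Only the fall below 66% comes from missing tracer pairs. With 64 patients and delta 0.423 L, power is about 62% at 90% uptake and 58% at 80%, so it passes below the SAP's lower figure of 60% somewhere between those two.

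**The case against.** The SAP already shows a case with losses: 60 evaluable patients is 26% fewer than 81, and 64 fully paired patients lie above it. The trial is exploratory. The current protocol makes no power claim, treats the primary pharmacodynamic analysis as descriptive (14.7.2) and labels the ANCOVA exploratory (14.7.3). Protocol 13.1.3.5 also says that a patient with a Day 1 tracer value should have the Day 14 one. The planned ANCOVA may be more efficient than the t-test behind the power figure, though the documents give no correlation from which to work that out.

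Most of this stands, and it limits the point to a stated figure that needs correcting. It does not remove it: the SAP still prints both powers, still ties them to pairs, and plans a one-sided 5% comparison (2.6.2). It also relies on interim sample size re-estimation, whereas current protocol 14.10 plans no interim analysis beyond the DMC safety reviews.

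Three stronger readings are tempting and unsupported:

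- *That the trial will be badly underpowered for plasma volume.* Uptake is not stated, so the lower rows of the table are possibilities, not forecasts.
- *That the protocol declares patients without a tracer pair evaluable.* Section 8.1 does not define the word. The replacement rules merely do not ask for a pair, and the pharmacodynamic population does require valid values at both visits.
- *That Day 14 losses fall on the sickest patients.* The amendment history (Appendix F, amendment 2) explains the transfer provisions by patients who may be in stable condition and getting better, and protocol 13.1.3.4 links some long hospital stays to local policy. Informative loss cannot be excluded, but the documents do not show it.

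**Conclusion.** The point holds as a mismatch between SAP 1.3 and the design now in force. With 64 patients the SAP's own assumptions give about 66% at best, not 71%. Power then depends on a number of tracer pairs that no rule fixes: about 55% at 75% uptake and about 43% at about half. At that last level the CI half-width (0.48 L) slightly exceeds even the printed 0.47 L effect. These figures rest on the derived 0.423 L, SD 0.8 L, equal uptake across arms and an unadjusted t-test. Taking 0.47 L instead raises them to 74%, 63% and 49%, but then the SAP's 71% and 60% no longer reproduce. The trial remains valid for its exploratory purpose; what needs correcting is the stated power.

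**What to change.** 1. In SAP 1.3, replace the 71% and 60% figures with a table of power and 90% CI half-width for the 64-patient allocation, by number of paired tracer completers. State the difference in litres that is used, and anchor the table with the blinded count of pairs already obtained in cohorts 1 and 2.
2. Align the replacement target in protocol 12.3 (81) with that in 8.1 (about 64), and define evaluable there, saying whether a tracer pair is needed.
3. Where feasible, choose the one to three cohort 3 centres from those able to run the tracer test.

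This takes a SAP revision, a short protocol correction and a site-selection preference, and adds no patients. The downside is a lower stated power. Patients may still decline the test, so the third step improves uptake without guaranteeing it; the table in the first step makes any shortfall visible.
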